## 12.4 Specification of assessments

## 12.4.1 MYD88 and CXCR4 mutational status

It is **obligatory** for the study to determine the mutational status of the following genes within 4 months prior to randomization into the study:

## • MYD88 (L265P) Mutation

## • CXCR4 Mutation

Known MYD88 mutation and CXCR4 mutation are mandatory for randomization into the study. Detection of MYD88 and CXCR4 mutations can be performed from peripheral blood or bone marrow. If mutations are not detected in the peripheral blood, a confirmation of the negative result is necessary by performing a mutational analysis from bone marrow cells (exclusion of false negative results).

## 12.4.2 Histopathology

#### 12.4.2.1 Histological material

The local histological examination of bone marrow biopsy must be performed within 4 months prior to randomization. Additionally, a pathological assessment will be performed by a designated reference pathologist (list in the ISF).

### 12.4.2.2 Pathological diagnosis

Inclusion of the patient in the study will be based on the pathological assessment and mutational status and the histopathological diagnosis of lymphoplasmacytic lymphoma (LPL), which is the underlying histology of WM.

Beside the local pathological assessment, a central pathological review will be organized for all patients included in the study at screening. The pathological review will be done nationally in each of the participating countries (if available) or in Germany.

The pathological review will be done without knowledge of patient outcome and will comprise the confirmation of the diagnosis of LPL. This pathological diagnosis is the basis of the diagnosis of WM, which is defined as LPL with bone marrow infiltration and an IgM monoclonal gammopathy of any concentration and requires therefore morphology, immunophenotyping from the bone marrow and IgM characterization.

For the diagnostics of LPL as the underlying histopathology of WM it is recommended that the following material is sent to the reference pathology:

- Bone marrow trephine ( $\geq$  1 cm) fixed in formalin (no other fixative)
- 4 bone marrow smears (air dried, unstained)
- 4 blood smears (air dried, unstained)

It is important to have a minimum of smears sent to pathology independent of whether the smears are also analyzed elsewhere to allow the hematopathologist to generate a report based on all morphological features including cytology on smears. Optionally the following material should be sent to the pathology:

• Any other biopsy specimen including lymph nodes

Furthermore, information about:

- year of birth, gender
- Monoclonal IgM gammopathy (yes / no)
- Previous hematological diseases
- Known MYD88 mutation yes / no
- Known CXCR4 mutation yes / no

should be sent to the pathology by using the appropriate form in the ISF. The mandatory diagnostic staining panel of the reference pathology will include:

• CD20, CD5, CD23, cyclin D1, Kappa, Lambda, IgM

with optional staining panels according to differential diagnosis in each individual case.

#### 12.4.3 Imaging

CT scans of neck, thorax and abdomen routinely performed within 3 months prior to randomization will be accepted for study inclusion. If there are contraindications against performing CT scans, MRI imaging is also accepted. All further imaging will be done as outlined in the flowcharts according standard of care every 6 months and only if initially positive.

#### 12.4.4 Patient demographics

Patient's demographics comprise year of birth, gender and childbearing potential.

#### 12.4.5 Medical history

At screening relevant medical history not pertaining to the study indication started within 5 years before signing informed consent and assessments of any current medical conditions that are considered relevant for the patient's study eligibility have to be documented in the eCRF.

#### **12.4.6 Previous therapies**

At screening previous therapies for WM will be documented in the eCRF. This includes name of therapies, number of cycles and start / stop date.

#### 12.4.7 Physical examination

Thorough physical examination includes, but is not limited to B-symptoms, cardiovascular, gastrointestinal, hepatobiliary, respiratory, skin, musculoskeletal, genitourinary / renal and neurological system. Physical examinations will be performed according to the flowcharts; relevant findings concerning these examinations will be documented in the eCRF at screening as medical history. A targeted physical examination to focus on areas involved by AEs or areas involved by WM (e.g. splenomegaly, lymphadenopathy) and for B-symptoms will be performed during further visits according to the flowcharts.

Height (cm) will only be measured at screening. Weight (kg) must be taken at screening and on day 1 of every cycle and results must be present on the patient's chart and recorded correspondingly into the eCRF.

The performance status will be done according to WHO / ECOG criteria (see appendix 21.2) during screening and thereafter on day 1 of every cycle.

### 12.4.8 Vital signs

Vital signs include heart rate, blood pressure and temperature.

### 12.4.9 Electrocardiogram (ECG) / transthoracic echocardiography (TTE)

A 12-lead ECG (including PR-, QT- and QTc interval) will be performed at screening and at visits according to the flowcharts. Each ECG tracing will be kept in the source documents at the investigational site.

Transthoracic echocardiography will be performed at screening and after that every 6 months (cycle 7, cycle 13, cycle 19, cycle 25 etc.) and if clinically indicated. Clinically significant abnormalities of ECG or TTE should be reported as medical history during screening or after that as AEs in the eCRF.

### 12.4.10 Pulmonary function test

A pulmonary function test will be performed at screening and thereafter only if clinically indicated. Only clinically significant abnormalities should be reported as medical history during screening and thereafter as AEs in the eCRF.

### 12.4.11 Fundoscopy (Ophthalmoscopy)

A fundoscopy will only be performed if hyperviscosity is suspected during screening visit. Clinically significant abnormalities should be documented in the medical history in the eCRF.

## 12.4.12 Laboratory tests (local laboratory at the site)

Blood tests and urinalysis include the routine parameter listed below and will be scheduled according to the laboratory flowcharts (see appendix 21.4 and 21.5) and in addition as clinically indicated. In case of cytopenia the frequency of blood samples would be increased from the 25th cycle (Arm A) and 14th cycle (Arm B) to once a month. Test results from the screening visit can be used for Cycle 1, day 1 in the discretion of the investigator (depending on local standards and e.g. the timeframe between screening laboratory and day 1).

#### 12.4.12.1 Pregnancy test

All women of childbearing potential (including those who have had a tubal ligation) will have a urine pregnancy test at screening, which has to be repeated 2 weeks after the first test to confirm results. After that monthly pregnancy tests are mandatory until 6 months after end of treatment. For patients who continue treatment after cycle 24 pregnancy test strips will be supplied by the sponsor.

### 12.4.12.2 Haematology

Complete blood count (CBC) including leucocytes, platelets, hemoglobin, erythrocytes, hematocrit and differentiation (absolute lymphocytes, monocytes, neutrophils, eosinophils, basophiles).

### 12.4.12.3 Serum chemistry and electrophoresis

Chemistry panel include sodium, potassium, calcium, creatinine, total bilirubin, SGOT, SGPT, LDH, magnesium, phosphate, glucose, urea / BUN, total protein, albumin, CRP.

ß2-microglobulin will be assessed at screening and after that every 6 months. Serum electrophoresis includes the M-protein and will be assesses at screening and after that every 6 months. A serum immunofixation must be performed at screening, cycle 13 and after that every 6 months.

### 12.4.12.4 Coagulation

Coagulation tests include INR and partial thromboplastin time (activated or not).

#### 12.4.12.5 Urine analysis

Urine status analysis include total protein and the Bence Jones protein.

#### 12.4.12.6 Quantitative immunoglobulins

Quantitative immunoglobulins include IgM, IgG and IgA.

#### 12.4.12.7 Free light chain

Free light chain panel include free kappa, free lambda and kappa / lambda ratio.

#### 12.4.12.8 Cryoglobulins

If cryoglobulinemia is suspected the following test will be done: cold agglutinin, direct Coombs test. Repeated assessments are only necessary if initially positive.

#### 12.4.12.9 Virology

Hepatitis B / C serologic markers and / or viral load and HIV will be tested at screening. Testing for HbsAg and anti-Hbc is obligatory for the Hepatitis B serology. In case the patient is positive for either HbsAg and / or anti-Hbc, patients can be only included if HBV-DNA is negative. In this case Hepatitis B prophylaxis has to be initiated and HBV-DNA in these patients needs to be re-evaluated in regular intervals according to local guidelines. It is also necessary to know if the patient was HBV-DNA positive in the past due to the risk of Hepatitis B reactivation (in this case

prophylaxis of HBV reactivation has to be initiated, see also section 11.4.1). Patients who are currently HBV-DNA positive at screening may not be included into the trial.

## 12.4.13 Staging and efficacy assessments

Response to treatment will be evaluated as indicated in Table 1 and Table 2 of the flowcharts. In case of response or stable disease, the next cycle will be delivered. Progression will be considered as treatment failure. In this case the patients will discontinue treatment and will enter survival follow-up. Modified response criteria as defined will be used for evaluating responses, identifying stable or progressive disease (appendix 21.1). After the first 12 months of treatment the response will be assessed prior to day 1 or at day 1 of cycle 13. CT scan in case of initial lymph node enlargement or splenomegaly, FACS analysis peripheral blood (B-NHL panel), bone marrow trephine biopsy, bone marrow smear and aspirate will be repeated at that time (bone marrow evaluation only for confirmation of complete response or documentation of delayed response). Best response within the time period between the beginning of treatment and end of follow-up should be documented for every patient. Therefore:

- Changes in the serum concentration of monoclonal immunoglobulin will be monitored with serum protein densitometry tracing (electrophoresis) (in particular if IgM monoclonal protein exceeds 5 g/dL) or by nephelometry. Sequential analyses of serum IgM should be performed using the same methodology in the same laboratory.
- 2. During the subsequent follow-up bone marrow trephine biopsy and bone marrow smears and aspirate is only mandatory to confirm complete response and CT scan (if contraindications MRI) only in case of abnormalities related to WM before initiation of therapy.
- 3. Serum protein electrophoresis, nephelometry or densitometry (whichever is used for an individual patient) and immunofixation have to be repeated at least 6 weeks later in case of complete response to confirm CR.

## 12.4.14 Assessments of Quality of life

The quality of life of the patients will be evaluated using the FACT-Lym questionnaire (see ISF). Questionnaires and all related subscales, translations, and adaptations are owned and copyrighted by [name]. This questionnaire is a validated and well-established scoring instrument to measure the management of chronic illness in lymphoma patients.

## 12.4.15 Concomitant medication

Only current concomitant medication and supportive care including hematopoietic stimulating factors at screening will be recorded into the eCRF. In the following cycles ongoing and new medication will be documented.

## 12.4.16 Biological sampling

The patient consent and signature on the informed consent for biosampling (if applicable in the participating country) is prerequisite for biological sampling. The procedures for the management of biological samples will be explained in appendix 21.3 and in the laboratory manual. If any patients will withdraw his / her consent to further biological sampling and storage during study participation, no further collection of biological samples will take place and already stored samples will be destroyed if possible and wished by the patient. This does not affect the patient's participation in the clinical study in any other respect.

## 12.5 Randomization Procedure

A stratified central block randomization will be used to allocate the patients 1:1 to the 2 arms. Stratification factors are MYD88 and CXCR4 status with the following groups: MYD88mut/CXCR4non-mut; MYD88mut/CXCR4mut; MYD88non-mut/CXCR4non-mut (MYD88non-mut/CXCR4mut not applicable) and number of prior lines (0 vs.  $\geq$  1 treatment lines). A stratification by site is not feasibly due to the rare disease status and the high number of sites (approximately 30 sites).

In this study an electronic randomization will be used. For electronic randomization each site will log on to the eCRF (only authorized personal). The questions for stratification factors and questions on inclusion / exclusion criteria have to be answered prior to randomization. The treatment arm assigned to the patient will be shown immediately and sent by e-mail to site personnel and sponsor in addition. A user manual describing the randomization and documentation process will be distributed to each site.

## 12.6 Patient study participation card

All participating patients will receive a study participation card, on which the study title and study drug are indicated. Furthermore, the address and telephone number of the local investigator is listed in case of emergency. The patients should always carry this card with them.

## 12.7 Criteria for premature discontinuation of the study

## 12.7.1 Early study termination for an individual patient

Patients can withdraw their informed consent to this study at any time and this does not interfere with their right of treatment by the local investigator. In case of cessation of the study-treatment a final statement concerning the treatment effect and the causes of premature study-termination have to be given by the investigator.

In case it becomes evident ex-post that a patient did not qualify for the study (e. g. did not fulfill all inclusion criteria or had an exclusion criterion at the time of randomization) the patient will
not be excluded from the study because the analysis of the study will be performed according to the intention-to-treat principle. In case that the patient has not completed the therapy according to the protocol of this study it is up to the local investigator to decide whether the patient should continue with the per-protocol therapy or not. However, the documentation of patients with ex-post non-qualification must continue as planned in the protocol.

The per-protocol treatment of the patient must be stopped for the following reasons:

- disease progression at any time;
- intercurrent illness that would, in the judgment of the investigator, affect assessment of clinical status to a significant degree;
- repeated clinically relevant violation of the protocol;
- non-compliance by the patient with protocol requirements;
- pregnancy;
- excessive and unexpected toxicity of the treatment;
- patient's decision to stop her / his treatment or participation in the study;
- decision by the local investigator for medical reasons;
- discontinuation of the study at the request of sponsor;
- Patient is lost to follow-up. If a patient does not return for scheduled visits, every effort should be made to re-establish contact (at least 3 attempts have to be documented in the source data). In any circumstance, every effort should be made to document patient outcome, if possible.

The reason for the early termination of the per-protocol treatment must be documented on the respective eCRF page. Patients who stop per-protocol therapy early must be documented and followed-up according to protocol. Early termination should be avoided. In case of an early termination of therapy, reasons / circumstances and if applicable the final disease status of the patient have to be documented. If the patient does not withdraw the consent for further follow-up, he or she should be followed-up as planned.

## 12.7.2 Early closing of a study site

The closing of a study site will be considered if:

- it does not meet the technical requirements of the protocol;
- the recruitment rate is not sufficient;
- inaccurate, incomplete or insufficient data collection and quality after repeated requests of the sponsor (GCP non-compliance);
- detected fraud;
- the conduct of the study is repeatedly not compliant with the protocol.

The early closing of a site will be decided by the coordinating investigator / sponsor and national co-coordinator. If an investigator of a site decides not to take part in the study any longer they have to inform the coordinating investigator immediately. The decision should be well-founded. Details on further treatment and follow-up of patients already on study are in the discretion of the investigator of the site.

## 12.7.3 Early termination of the study

Early termination of the entire study may be necessary for the following reasons:

- the occurrence of serious unexpected side effects of treatment;
- excessive treatment-related mortality;
- relevant pertaining new information from other studies or publications;
- inadequate recruitment rate in the whole study;
- excessive number of deviations from the study protocol in the whole study;
- any other fact which would change the risk-benefit analysis of this study.

Any premature discontinuation will be appropriately documented according to local requirements (e.g. EC, regulatory authorities, etc.).

The DSMC will monitor the study conduct and the safety aspects of the study as described in section 15 and will give recommendations to the coordinating investigator / sponsor of the study whether to stop the study or to change the study protocol. The coordinating investigator / sponsor will then decide on the actions to be taken. The decision on an early termination of the study is a complex action which has to consider in addition to statistical also medical and ethical as well as organizational and financial aspects. Finally, according to the national drug laws, the study may be suspended or early terminated by decision of the respective competent authorities. All CAs and the ECs in charge will be notified about the early termination of the study.

## 13. ASSESSMENT OF SAFETY

## 13.1 Closer monitoring of the first 10 patients in arm A

Both study medications are not approved in the study indication in this combination. Therefore, it will be a close monitoring for treatment related toxicity comprising the first 10 included patients into the study in arm A. Safety evaluations will be performed on day 1, day 8 and day 15 for cycle 1-6 (more details about the assessments will be found in section 12.2).

## 13.2 Monitoring, recording and reporting of adverse events

All patients will be monitored for AEs during the study. Assessments may include monitoring of the following parameters: the patient's clinical symptoms, laboratory, pathological, radiological or surgical findings, physical examination findings or other appropriate tests and procedures.

All adverse events, serious adverse events and special reporting situations, whether serious or non-serious, will be recorded from the time of first application / intake of IMPs until the patient's end of treatment visit (30 days after last intake of study drug). Additionally, all kinds of secondary malignancies have to be reported until end of study.

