Follow Up will be done in the first two years every 3 months, after that every 6 months for three years. At time of progressive disease at any time during the study the assessments below has to be performed. After progression of disease or start of new anti-lymphoma therapy patients will be followed up for survival only. Within the study the follow up period is maximum 7 years after first patient in. All assessments listed in Table 3 are performed within routine on standard WM follow up.

PERIODS	Name		Every 3 months 1 st 2	Every 6
	Duration		years, after that every 6 months for 3 years (± 14 days)	months (± 14 days)
VISITS		Progress	FU Visit(s) 	S- FU #
	Time Section	anytime	After end of treatment visit	After pro- gression or start of new WM therapy
Administrative procedure				
Molecular analysis: MYD88 and CXCR4 Mutational Status 	12.4.1		as clinically indicated	
Clinical assessments				
Targeted physical examination 	12.4.7	х	Х	
WHO / ECOG Performance status	12.4.7	Х	Х	
Laboratory assessments (local laboratory)				
Pregnancy test (only WCBP)	12.4.12.1		x 	
Hematology with diff	12.4.12.2	х	x	
Serum chemistry and electrophoresis 	12.4.12.3	Х	X 	
β2-microglobulin⁵	12.4.12.3	Х	X 	
Coagulation 	12.4.12.4	Х		
Quantitative immunoglobulins	12.4.12.6	Х	Х	
Free light chain	12.4.12.7	Х		
Staging and efficacy assessments			•	
CT neck / thorax / abdomen 		Х	X°	
Bone marrow aspiration and - biopsy with flow cytometry and FACS peripheral blood	12.4.13	Х		
Further assessments				
FACT-Lym questionnaire	12.4.14	Х	X°	
Concomitant medication	12.4.15	Х		
Adverse events	13	Х		
New anti-lymphoma treatment and survival		Х	x	Х

Every 6 months

 Assessment of mutational status only as clinically indicated.

 A targeted physical examination to focus on areas involved by AEs or areas involved by WM (e.g. splenomegaly, lymphadenopathy) and for B-symptoms.

 Monthly for the first 6 months after end of treatment (will be provided by the Sponsor).

 Serum chemistry (sodium, potassium, calcium, creatinine, total bilirubin, SGOT, SGPT, LDH, magnesium, phosphate, glucose, urea / BUN, CRP, total protein, albumin). Serum electrophoresis will be done only every 6 months.

β2-microglobulin will be done every 6 months.

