## 8.5 Safety endpoints

Safety variables will include AEs, SAEs, laboratory parameters, ECG and vital signs. The severity of AEs will be graded using the NCI-CTCAE version 5.0 dictionary. An AE is defined as any event arising or worsening after first application / intake of study drug until 30 days after the last study drug intake. Safety variables will be summarized by means of descriptive statistics and / or frequency tables as appropriate. All AEs, drug related AEs and serious AEs will be summarized by MedDRA classification and worst CTCAE grade.

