## 12. STUDY ASSESSMENTS

A detailed flowchart is provided in Table 1, Table 2 and Table 3 in the synopsis. The schedule of assessment lists all of the assessments and indicates with an "x" when they have to be performed. All data obtained from these assessments must be available in the patient's source documentation. During the course of the study, visits and test procedures should occur on schedule whenever possible; visits that occur  $\pm 4$  days (during treatment, further time window sees flowchart) from the scheduled date will not constitute any protocol deviation.

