## 12.3 Follow up phase

As soon as the treatment is stopped because of non-tolerated toxicity, patients will enter followup and will be clinically evaluated every 3 months after the last treatment for 2 years and then every 6 months for 3 additional years or until progression of disease (until end of study).

Patients with progression or starting of new anti-lymphoma therapy will be followed up only for survival data and data with regard to further treatment of WM every 6 months until end of study.

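### Section 13.2 requires secondary malignancies to be reported until end of study, but section 12.3 and Table 3 schedule no collection of them at follow-up visits or survival contacts

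*Protocol*

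**What the plan says.** The duty is in section 13.2. Adverse events, serious adverse events and special situations are recorded from first intake until the end-of-treatment visit, and then comes the exception: "Additionally, all kinds of secondary malignancies have to be reported until end of study". It carries no condition on causality or on the phase the patient is in.

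The follow-up arrangements read differently:

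- Section 12.3, for patients after progression or a new lymphoma therapy: they "will be followed up only for survival data and data with regard to further treatment of WM every 6 months until end of study".
- Introduction to Table 3, for the same patients: "After progression of disease or start of new anti-lymphoma therapy patients will be followed up for survival only".
- Table 3, adverse-event row: one mark, under the progression assessment. The columns for follow-up visits and survival follow-up are blank in that row, and no row names secondary malignancies.
- Section 12, on the status of the flowcharts: "The schedule of assessment lists all of the assessments and indicates with an" x when each is due.
- Section 13.7: a serious adverse event beyond 30 days after the last intake is reported if it is considered related to the study drugs.
- Section 8.5: an adverse event is one "arising or worsening after first application / intake of study drug until 30 days after the last study drug intake".

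The safety paragraph of the synopsis (section 5) also ends adverse-event collection at the end-of-treatment visit and does not mention the exception.

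**The concern.** The sponsor decided that second cancers need observation beyond the usual 30-day window, for every patient and whatever the cause. The documents that tell a site what to ask after treatment do not reflect that decision. For a patient who has progressed or started a new therapy, a site that follows the word *only* in section 12.3 literally would not collect what section 13.2 requires. For a patient who stopped for toxicity and is in regular follow-up, nothing forbids the question, but nothing prompts it either.

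At stake is how completely second cancers are counted in a trial of a combination that, by section 13.1, is not approved in this indication, with observation of up to 7 years. Cases not asked about at the time may be hard to recover once follow-up has closed. The primary endpoint, the sample size and the planned DSMC reviews do not depend on this.

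**Working it through.** The plan gives no figure for this point, so there is none to reproduce. The check is a comparison of the passages by phase, followed by an indication of scale.

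**1. Passages side by side**

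| Phase | Section 13.2 requires second cancers? | What the schedule collects |
|---|---|---|
| On treatment to 30 days after last dose | Yes | Adverse events continuously (Tables 1 and 2): covered |
| Progression assessment, any time | Yes | Adverse events marked in Table 3: covered at that visit |
| Follow-up visits (stopped for toxicity) | Yes | Targeted examination, performance status, laboratory tests, imaging, FACT-Lym, new treatment and survival; no adverse-event or malignancy item |
| Survival follow-up (after progression or new therapy) | Yes | New treatment and survival only, by phone or on site; section 12.3 says *only* |

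The last row is a contradiction in wording. The third is a requirement without a scheduled item. Section 13.7 does not close either gap: its late rule is limited to serious events considered related, while section 13.2 covers all kinds of second cancer. A second cancer judged unrelated, arising after the 30-day window, rests on the one sentence in section 13.2.

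**2. Calendar from the Protocol's dates (sections 5 and 9.1)**

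First patient 18.02.2021; end of study at most 7 years later, i.e. 18.02.2028; last patient in Q2 2024. Time from inclusion to the latest end of study:

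- first patient: 7 years (84 months);
- patient included 01.04.2024: about 3.9 years;
- patient included 30.06.2024: about 3.6 years.

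The accrual period is thus about 40 months.

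**3. Person-time in the uncovered period**

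Inputs from the Protocol: 99 patients, accrual about 40 months, end at 84 months. Assumptions, not in the Protocol: uniform accrual, constant mortality m = 0.03 per year, constant rate d of stopping all study treatment of 0.08, 0.12, 0.18 or 0.25 per year.

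Potential observation U is uniform between a = 44/12 = 3.667 and b = 7 years.

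Total person-years = 99 × (1/m) × [1 − (e^(−ma) − e^(−mb)) / (m(b − a))]
= 99 × (1/0.03) × [1 − (0.8958 − 0.8106)/0.100]
= 99 × 4.917 ≈ 487.

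Person-years more than 30 days (1/12 year) after last dose = 99 × mean over U of ∫ from 1/12 to U of e^(−mt) × (1 − e^(−d(t − 1/12))) dt.

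| d per year | Person-years beyond 30 days | Share of 487 |
|---|---|---|
| 0.08 | 87.5 | 18% |
| 0.12 | 122.8 | 25% |
| 0.18 | 167.6 | 34% |
| 0.25 | 209.9 | 43% |

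This is time during which no scheduled item asks about second cancers, apart from a progression assessment that falls within it (not subtracted here). It is not an estimate of cancers missed.

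**The case against.** The strongest reply is that section 13.2 is a mandatory reporting duty, and a duty to report need not appear in a visit grid. Sites stay in contact in both phases, so they can comply. Other routes exist as well: related late serious events stay reportable without time limit, and section 13.4.3 sets a low threshold for related; adverse events are marked at progression; cause-specific survival (section 14.1.2) needs the cause of death, so fatal second cancers should surface. The eCRF is not shown and may hold such an item.

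Much of this stands, and it rules out several stronger readings that a reader might infer:

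- *That late second cancers are missed.* The duty remains in force and sites may report unprompted. The documents support only that collection is not systematic and that cases may be missed.
- *That regular follow-up visits record nothing but new treatment and survival.* That is true of survival follow-up only. Regular visits include examination, laboratory tests, imaging and a questionnaire; they lack the specific item, not clinical contact.
- *That 18 to 43% of second cancers would be lost.* This would need a constant cancer rate and no reporting at all after treatment.
- *That the under-count differs between the arms.* The Protocol gives neither direction nor size. By sections 11.1 and 11.3.2.1, stopping one drug in arm A does not end treatment, so stopping Carfilzomib alone does not start the uncovered period.
- *That the 30-day window in section 8.5 is itself an error because no separate summary of late malignancies is described.* Section 8.5 gives the general rule and section 13.2 an express addition; the table that presents the late cases can be left to the SAP.

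The objection does not remove the word *only* in section 12.3 or the narrower wording above Table 3. Neither can be followed literally together with section 13.2 for the same patient, and no other passage reconciles them. Cancers that are neither fatal nor judged related still depend on a single sentence.

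**Conclusion.** The inconsistency is real. Section 13.2 requires all second cancers until end of study. Section 12.3 and the introduction to Table 3 exclude them by their wording after progression or new therapy, and Table 3 has no item for them at follow-up visits or survival contacts. Second cancers arising more than 30 days after the last dose, especially those judged unrelated, are not systematically collected and may be under-ascertained.

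The person-time concerned is 18 to 43% of about 487 person-years for assumed discontinuation of 8 to 25% per year and mortality of 3% per year. Both rates are assumptions. If the cancer rate is constant over time, the share is an upper bound on the proportion of cases missed; the true loss depends on how well sites follow section 13.2 without a prompt, which the Protocol cannot tell us.

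This should be corrected because it weakens a safety requirement that the Protocol sets itself. It does not threaten the primary analysis.

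**What to change.** Reconcile the passages in favour of the requirement already in section 13.2:

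1. Table 3: add a row *secondary malignancy (yes/no, type, date)*, marked for follow-up visits and for survival follow-up.
2. Section 12.3: name secondary malignancies among the data collected until end of study, beside survival and further WM treatment.
3. Introduction to Table 3: make the same addition, so that it agrees with sections 12.3 and 13.2.

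The cost is a minor amendment and one eCRF item at visits or phone calls that already take place. No visit, test or treatment changes.
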